2. The articles were analyzed only if the use of a collagen membrane in these strategies was clearly indicated. Even if the final outcome was not to assess safety the collagen membrane per se, the absence of complications related to the strategy can be extended to the use of the collagen membrane as well. Thus, all studies were kept in the safety analysis.

3. The minimal clinical follow up taking into account soft tissue healing was 3 months to have reliable data.

4. Most of the studies have been conducted following the best required methodology (prospective randomized study, or prospective comparative study) to assess performance and safety of a product (level I). The other prospective and retrospective (clinical cases) studies (level II & III) are less appropriate because of the lack of methodological design (no comparison) and only descriptive statistics (or unique case), but the most interesting informations were kept in the clinical review.

5. Split mouth approach was often used to compare different approaches within the same patient and to increase the number of cases in the same study.

6. Moreover, in periodontal applications, main results concern radiological and histological assessments that are not clinical outcomes; it is the most usual way to address this question in these indications.

II.3.STUDY HYPOTHESES

Based upon previous data collected in the literature [3, 5, 10, 11, 17, 18] and previous experience with the Biomatlante RCM, the hypothesis that justifies this research is that 90% of the patients who will undergo GTR and/or GBR involving the RCM in oral/maxillofacial defects will show tissue regeneration at 12 weeks after surgery, as assessed by observation of :

- Tissue regeneration (mucosa health on the implantation site)
- Safety report on any adverse event
- Height preservation of the alveolar crest

II.4. JUSTIFICATION OF METHODOLOGY CHOICES

Regarding:

- the number of RCM units commercialized,
- the ability of the centers to recruit and appropriately record follow-up data,
- the previous data about the principal criterion,
- the follow-up duration of the patients

The sponsor expects that a prospective observational study will allow gathering the data required in terms of performance, and safety in a 22 months delay.

II.5.EXPECTED IMPACTS

This study will confirm the performance and safety of the RCM in periondontal defects and its acceptable benefit/risk balance.

III. OBJECTIVES

III.1. MAIN OBJECTIVE

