The main objective of this study is to observe performance of the RCM in terms of periodontal tissue regeneration by the observation of mucosa health in terms of swelling, wound closure and colour of the implantation site

III.2. SECONDARY OBJECTIVES

The secondary objectives are:

- Evaluation of the safety of RCM by recording all the adverse events during the follow-up
- Evaluation of the radiographic analysis of periodontal tissues

IV. STUDY DESIGN

IV.1. CLASSIFICATION OF THE STUDY

This clinical investigation is prospective, multicentric, single arm and non-comparative.

The study is classified as category 3 according to the Jardé Law (French Law relative to the Clinical Research Involving Human Persons) and thus is qualified as "non-interventional".

Indeed, according to the terms of the protocol established in collaboration with the stakeholders, this research will be carried out on a CE-marked device (CE 0123) and does not involve any risk or constraint since all the procedures will be performed and the products used in a usual way, without any additional or unusual diagnostic, treatment or monitoring action.

IV.2. RESEARCH PROJECT AGENDA

- Duration of the inclusion period: 18 months
- Duration of follow-up per participant: 12 weeks (± 1 week)
- Total duration of the research project: 22 months

	Pre-inclusion V -1	Inclusion V 0	Visit V 1 At 1 week	Visit V 2 At 2 weeks	Visit V 3 At 12 weeks
	-1 month to Day 0	Day 0	$\pm 2 \text{ days}$	$\pm 2 \text{ days}$	± 1 week
Full information and non-opposition	✓				
Inclusion / Exclusion criteria	✓				
Demographic data ^(a)	✓				
Life habits (smoker)	✓				
Relevant medical and surgical histories	✓				
Periodontal clinical examination ^(b)	✓				
PROCEDURE			- -	- -	
Batch		√			
Clinical indication		√			
Usability		√			
CLINICAL EXAM			-	-	
Control of tissue regeneration (c)		√	✓	✓	✓
Membrane performance ^(d)			√	✓	✓
SAFETY			•	•	

IV.3. SUMMARY TABLE OF PARTICIPANT FOLLOW-UP

	Pre-inclusion V -1	Inclusion V 0	Visit V 1 At 1 week	Visit V 2 At 2 weeks	Visit V 3 At 12 weeks
	-1 month to Day 0	Day 0	$\pm 2 \text{ days}$	$\pm 2 \text{ days}$	± 1 week
Adverse events recording	✓ <				> ✓
X-RAY					
Probing Pocket Depth (PPD)	√ *	√*			✓
Clinical Attachment Level (CAL)	√ *	√ *			✓

(a) Demographic data: age, sex

(b) Periodontal clinical examination: in accordance with the current practice (e.g. Probing Pocket Depth (PPD) using sensor and search for gingival inflammatory signs)

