- (c) Control of tissue regeneration: swelling, wound closure, colour of the implantation site
- (d) Membrane performance: barrier effect, membrane exposition

* X-Ray performed at pre-inclusion or inclusion visit (before the surgery)

IV.4. INFORMATION TO PARTICIPANTS

During pre-inclusion visit, the Investigator (a qualified individual) will ask the participant and/or the legal guardians/legal representative to participate in the research project and provide him/her/them with information regarding:

- The objective, the description of the surgery and,
- The automatic processing of participant-related data that will be collected during the research project, and shall also specify the participant's right to access, object to, or rectify the data.

The Investigator will also ensure that the eligibility criteria are met. If a person agrees to participate, he or she will sign the consent form included at the end of the patient information sheet. His or her non-opposition to data use will be recorded and stored in his or her medical file. The participant may, at any moment, oppose the use of his or her data as part of the research.

IV.5. FOLLOW-UP VISITS

- V -1, pre-inclusion visit (-1 month to Day 0):
 - Signature of the written consent
 - Inclusion / Exclusion criteria
 - Demographic data
 - Life habits: smoker
 - Relevant medical and surgical histories
 - X-Ray

- Periodontal clinical examination
- V 0, inclusion visit:
 - X-Ray (Pre-surgery, if not performed at pre-inclusion visit)
 - Periodontal surgery, tooth extraction, alveolar filling
 - Evaluation of product stability and usability
 - Safety evaluation by the record of any adverse event
- V 1 and V 2 at 1, 2 weeks post-surgery (\pm 2 days):
 - Control of soft tissue regeneration
 - Membrane performance
 - Safety evaluation by the record of any adverse event

IV.6. END OF RESEARCH PROJECT VISIT

- V 3 at 12 weeks (± 1 week):
 - Control of soft tissue regeneration
 - Membrane performance
 - X-Ray
 - Safety evaluation by the record of any adverse event

V. STUDY POPULATION

V.1. INCLUSION CRITERIA

- Male or female aged 18 to 70
- Periodontal defects (e.g. cyst, bone tumour, crest augmentation...)
- Alveolar bone defect after tooth (teeth) extraction
- Non Opposition form (consent of the patient)
- Patients affiliated to the French social security
- Patients not under guardianship or judicial protection

V.2. EXCLUSION CRITERIA

- Pregnancy or breastfeeding women

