- Severe smoker (>10 cigarettes per day)

- Acute infections.
- Allergies to the material (if an allergy of any kind is suspected, adequate exams must be carried out in advance)
- Refusal of the patient to adhere to surgical follow-up and to the limit in activity level
- Fever and/or local inflammation
- HIV positive known
- History of uncontrolled diabetes (untreated or not stabilized by treatment)
- History of treatments for previous corticosteroids, long-term (more than 6 months) and interrupted for less than 3 months
- History of chemotherapy in progress or during the last three months
- History of cervico-facial radiotherapy
- History of bone disease with disorders of blood circulation which is defined as Albers-Schönberg disease or Paget's disease
- Known severe hyperparathyroidism
- History of severe immune deficiency

V.3. FEASIBILITY AND RECRUITMENT PROCEDURES

Coordinating Investigator

[name], PhD, Doctor of Dental Surgery (DDS) Associate professor Dental Faculty Nantes University Hospital, France.

Other Investigators

- [name], PhD, DDS, Associate professor Dental Faculty Nantes University Hospital, France.
- [name], PUPH, PhD, DDS, Dental Faculty Nantes University Hospital, France.
- [name], PUPH, PhD, DDS, Dental Faculty Nantes University Hospital, France.

Centers involved in the clinical investigation

Two centers will be involved in the clinical study. They already use Biomatlante RCM for GBR and GTR in oral/maxillofacial bone defects:

	Center n°1: Dental Care Center - Nantes University Hospital	Center n°2 Private Dental Practice – [name]	
Principal Investigator	[name]	[name]	
	[name]		
Investigators	[name]		
	[name]		

Each center will perform treatment in oral maxillofacial defects and will participate to patient recruitment during the whole study. The patients will be recruited during the consultations.

V.4. ACTIONS UPON PATIENT WITHDRAWAL

If a patient withdraws prematurely from the study, study personnel should make every effort to complete the full panel of assessments scheduled until the 12-week visit. The reason for patient withdrawal must be documented in the electronic case report form (eCRF).

Participation of a patient in this clinical study may be discontinued for any of the following reasons:

- The patient withdraws consent or requests discontinuation from the study for any reason;

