The Resorbable Collagen Membrane should be handled in accordance with the manufacturer's recommendation using gloves and/or sterile instruments. This membrane can be cut to the appropriate shape and can be used directly or previously hydrated to facilitate its handling, especially when the surgeon intends to shape or fold the membrane at the implantation site.

The Resorbable Collagen Membrane can be sutured for better immobilization. The manufacturer recommends that the implant site be completely closed to avoid exposure of the Resorbable Collagen Membrane.

VI.4. CONTRAINDICATIONS

- Acute infections
- Known collagen allergies (if any type of allergy is suspected, adequate tests should be performed in advance)
- Fever and/or local inflammation

VI.5. AUTHORIZED OR FORBIDDEN TREATMENTS AND PROCEDURES

No prior or concomitant medication will be prohibited.

VII. STUDY ASSESSMENTS AND PROCEDURES

VII.1. MAIN EVALUATION CRITERION

This principal objective is to observe the performance of the RCM at 1, 2 and 12 weeks post surgery in terms of tissue regeneration. It will be assessed by the evaluation of mucose health on the implantation site at the different times of follow-up. The mucosa aspects that will be reported are the following: swelling, wound closure and colour.

- Swelling is defined by the presence of one or more swellings in the wound. The total absence of swelling at 12 weeks will be considered as the efficacy endpoint. This swelling is assessed subjectively by the investigator with the naked eye or by photography.
- Mucosal healing is characterized by wound closure. Complete wound closure will be considered as the efficacy criterion. This wound closure is assessed subjectively by the investigator with the naked eye or by photography.
- The colour at the implantation site can take on 3 aspects: pink identical to the surrounding mucosa Red. Pink colours and identical to the surrounding mucosa will be considered as the efficacy criteria. This colour is assessed subjectively by the investigator with the naked eye or by photography.

VII.2. SECONDARY EVALUATION CRITERIA

The secondary ojectives are to evaluate the safety of the RCM during the 12 weeks follow-up and evaluate the radiographic analysis of periodontal tissues.

The evaluation of the safety will be conducted by recording all the adverse events from screening through the 12-week visit (12 weeks \pm 1 week).

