A new fact is defined as any new safety data which may lead to a reassessment of the relationship between the benefits and risks balance of the research or the product being investigated, changes in the use of the product, the conduct of the research or documents relating to the search, or to suspend or interrupt or modify the protocol of the search or similar searches. (R.1123-46 of the French Public Health Code).

In the case of a new medical fact, the Sponsor, will be responsible for reporting new facts to the authorities in accordance with national regulations, as follows:

- Inform without delay the ANSM about the new medical fact, at the following email address: [contact] with the following subject: Fait nouveau / trial number/ international non-proprietary name (INN) or substance code and including:
 - - ID-RCB N°,
 - - Title of the study protocol,
 - - Protocol code number,
 - - Summary of the new fact and urgent safety measures implemented if necessary,
 - All relevant information for the evaluation of the new fact.
- Inform without delay the director of the Agence Régionale de Santé (ARS; regional health agency) and the Ethical Committee (CPP).

Any follow-up information with regards to the new safety medical fact will be reported to the regulatory authorities within 8 calendar days, and details regarding the urgent safety measures set up will be sent within 15 days to the regulatory authorities.

VIII. STATISTICAL ASPECTS

VIII.1. SAMPLE SIZE DETERMINATION

As the study is descriptive, the calculation of study size is not calculated based on considerations relating to formal hypothesis tests. The required number of patients is calculated to guarantee that the endpoints associated with the main objective of the study could be estimated with sufficient precision.

The choice of a target of 90% of patients with tissue and bone regeneration at 12 weeks post-surgery is based on an estimation of the kinetics of reconstruction according to the literature (similar products resorbable membrane but with or without filling with different bone substitute) [3, 5, 10, 11, 17, 18, 20]. The score will be from 88.8% to 100% with follow-up from 4 to 12 months (due to evaluation of the bone void filler and not only the collagene membrane).

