For the primary endpoint of effectiveness as measured by the performance of the RCM (binary endpoint) with a 90% target frequency (as hypothesized) and a confidence level of 95%, the following precisions can be achieved. The calculation was made using SAS[®].

Precision	Target frequency of performance	Number of patients to evaluate	Number of patients to recruit
8.3%	90%	50	56
6.8%	90%	75	83
5.9%	90%	100	111
5.3%	90%	125	139
5.0%	90%	150	165

Table 2 Sample size determination

With 50 patients, a precision around 8.3% can be achieved.

Accounting for a maximum of 10% dropouts or missing data, 56 patients should be recruited in the cohort.

VIII.2. ANALYSIS SETS

Four populations will be defined:

- Screened population will include all patients entering the study,
- Safety Set (SS) population will include all patients who received the RCM product,
- Full Analysis Set (FAS) efficacy population will include all patients who received the RCM product and in whom at least one efficacy information has been collected after the application of the RCM,
- Per-Protocol (PP) efficacy population will include all patients in FAS population without any major protocol deviation.

Remark: according to the ICH E9 recommendations, this subset of patients corresponds to a subset of the full "intention-to-treat" analysis set (including all randomized patients), being the full analysis set (FAS).

VIII.3. MISSING VALUES AND DROP-OUT

For the primary analysis (FAS analysis), a patient with missing data on the one of primary efficacy endpoint (swelling, wound closure or colour of the implantation site) will be considered as non efficacy of the product for this patient. Sensitivity analyses will be performed according to the following scenarios:

- No missing data will be imputed
- The missing data for the one of primary efficacy endpoint (swelling, wound closure or colour of the implantation site) will be considered as efficacy of the product.

VIII.4. STATISTICAL ANALYSIS

VIII.4.1. GENERAL CONSIDERATION

A Statistical Analysis Plan will be written by the biostatistician detailing the statistical analysis. The document will constitute the reference document as far as statistical analyses and methodologies are concerned. This document will be approved and signed by the Sponsor and the Principal Investigator before the first database lock.

The statistical analysis will be performed on SAS® version 9.4 or later (or equivalent statistical software).

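### The primary composite measures mucosal healing only, so its response rate cannot be read as a rate of tissue and bone regeneration

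*Combined protocol and SAP*

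**What the plan says.** **What is scored.** VII.1 gives three components, each judged subjectively by the investigator by eye or on a photograph. For swelling, "The total absence of swelling at 12 weeks will be considered as the efficacy endpoint". The other two are complete wound closure and a colour that is pink or the same as the surrounding mucosa. VIII.4.2 counts the product as efficacious for a patient only if all three are met. Footnote (c) to the schedule in IV.3 lists the same items: "Control of tissue regeneration: swelling, wound closure, colour of the implantation site".

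**What it is called.**
- III.1 states the main objective as performance in terms of "periodontal tissue regeneration by the observation of mucosa health in terms of swelling, wound closure and colour of the implantation site".
- II.3 hypothesises that 90% of patients "will show tissue regeneration at 12 weeks after surgery". Among the things by which this is assessed, it lists preservation of alveolar crest height.
- VIII.1 sets the 90% target for patients with regeneration of tissue and of bone at 12 weeks, then sizes the binary primary endpoint "with a 90% target frequency (as hypothesized) and a confidence level of 95" per cent.
- The synopsis, under expected impacts, says the study will confirm the membrane's ability to promote guided tissue regeneration within 12 weeks.

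**What is measured elsewhere.** Barrier effect and membrane exposure are recorded at V1 to V3 (IV.3, footnote (d)). Probing pocket depth (PPD) and clinical attachment level (CAL) belong to the secondary radiographic evaluation, made before surgery and at 12 weeks (VII.2). VIII.4.4 reports it in a document separate from the statistical report.

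**The concern.** The hypothesis, the target and the expected conclusion are worded as regeneration. The responder rule records only whether the mucosa over the site looks healed. A patient who gains no bone and no attachment, but whose incision has closed without swelling or redness, is a primary-endpoint success.

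If about 90% of patients meet the composite, the plan as written invites the statement that tissue and bone regenerated in about 90% of patients. The primary endpoint holds no information on bone or attachment, so that statement would not follow. A historical benchmark on the same endpoint would not help, because it too would be a benchmark for mucosal healing. The point is therefore separate from the absence of a control arm.

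**Working it through.** **1. The plan's own figure.** Inputs from VIII.1: target p = 0.90, n = 50 evaluable, 95% confidence, 10% dropout.
- Half-width = 1.96 × √(0.90 × 0.10 / 50) = 0.083, that is ±8.3%, as stated.
- Recruitment = 50 / 0.9 = 55.6, rounded up to 56, as stated.

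The arithmetic is sound. VIII.1 also says that "the calculation of study size is not calculated based on considerations relating to formal hypothesis tests", so the 90% is a planning value for precision and not a null or benchmark. The ±8.3% describes how well the composite's rate is estimated. It says nothing about what that rate represents.

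**2. Components against labels.**

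| Place | What it refers to | Bone or attachment included? |
|---|---|---|
| VII.1, VIII.4.2 (responder rule) | Swelling, wound closure, colour | No |
| III.1 (objective) | Tissue regeneration, through mucosa health | No |
| Table 1 (literature behind the 90%) | Soft tissue healing, 81.2% to 100% | No |
| II.3 (hypothesis) | Tissue regeneration, with crest height among the observations | Yes |
| VIII.1 (90% target) | Tissue and bone regeneration | Yes |
| Synopsis, expected impacts | Promotion of guided tissue regeneration | Implied |

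The unweighted mean of Table 1 is (100 + 88.5 + 100 + 100 + 81.2 + 89.5 + 87) / 7 = 92.3%. A 90% planning value is in line with the table as a soft tissue healing rate. The table does not report a bone regeneration rate.

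**3. What an observed rate can say about regeneration.** Let r be the true proportion with regeneration, s the probability of meeting the composite if regeneration occurred, and f the probability of meeting it if not. Then

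observed rate = r × s + (1 − r) × f.

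The documents give neither s nor f. Take s = 1 as an assumption and let f vary. An observed 90% then fits:
- f = 0: r = 0.90
- f = 0.8: r = 0.50, since 0.50 + 0.50 × 0.8 = 0.90
- f = 0.9: r = 0, since 0 + 1 × 0.9 = 0.90

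These values show only that r cannot be recovered from the composite. They are not estimates of what will happen in this study.

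**The case against.** The strongest reply is that the protocol defines its terms. III.1 states regeneration through the observation of mucosa health, and the synopsis and II.3 add the same gloss in brackets. IV.5 and IV.6 speak of control of soft tissue regeneration, and Table 1 is about soft tissue healing. Bone and attachment are not ignored: PPD and CAL are scheduled, II.3 lists crest height as a separate item, and barrier effect is recorded. On this view a careful reader knows what is measured.

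Most of that stands, and it limits the point to labels, target and conclusion. It does not rescue VIII.1, which names bone in the target for an endpoint that has no bone component. Nor does it rescue the synopsis, whose expected conclusion goes beyond mucosal healing.

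Two stronger readings are tempting, and the documents support neither.

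- *A reader might infer that the success state is already fixed at entry and by closure at surgery.* V.2 excludes "Fever and/or local inflammation" but names neither swelling nor colour, and cysts and bone tumours are eligible. VI.3 makes suturing of the membrane optional, and closure of the site is advice: "The manufacturer recommends that the implant site be completely closed to avoid exposure of the Resorbable Collagen Membrane". Surgery comes between eligibility and the 12-week reading, and the review summarised in II.2 notes that membrane exposure was common. Healthy mucosa before surgery is likely, but it is not imposed, and closure can be lost. Scoring the composite before surgery would not settle the matter either: VII.1 defines swelling as in the wound and healing by wound closure, so on intact mucosa these items have no defined value.
- *A reader might infer that some particular share of patients, even about 90%, would succeed with no regeneration.* No such rate is given. Any figure would come from assumed healing and misreading rates, and Table 1 itself reports soft tissue healing as low as 81.2%.

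**Conclusion.** The point holds as a mismatch between what the primary endpoint measures and what the hypothesis, target and expected conclusion say about it. The composite is a usable measure of uncomplicated soft tissue healing, and the sample size gives the stated precision for that rate. It cannot be reported as a rate of tissue and bone regeneration.

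The conclusion rests on the wording of VII.1, VIII.4.2, II.3, VIII.1 and the synopsis, not on an assumed rate. Its size in percentage points is unknown and should not be given. The correction should be made before results are reported. It does not invalidate the study.

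**What to change.** 1. In II.3, III.1, VII.1, VIII.1 and VIII.4.2, name the primary endpoint and its 90% target *healthy mucosa (soft tissue healing) at 12 weeks*. This agrees with what Table 1 reports. It also states the visit for all three components: VII.1 attaches 12 weeks explicitly only to swelling, and VIII.4.2 names no visit.
2. State in VIII.4.2 that this endpoint does not by itself show tissue or bone regeneration, and bring the expected impacts in the synopsis into line.
3. Base any statement about regeneration on the change from pre-surgery to 12 weeks in the radiographic measures: PPD, CAL and alveolar crest height. The films, PPD and CAL are already scheduled at both times. Crest height is named in II.3 but has no line of its own in IV.3, so the plan should say that it is read from the same films. Because VIII.4.4 puts these results in a separate document, the statistical report should refer to it wherever regeneration is discussed.

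This needs no extra visit, patient or procedure. The cost is redrafting and a narrower headline claim.

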Justification / context	The evaluation of the clinical data has demonstrated the conformity of the Resorbable Collagen Membrane (RCM), EZ Cure TM , with the relevant essential requirements for its use in periodontal applications. The RCM is intended for Guided Tissue Regeneration (GTR) and Guided Bone Regeneration (GBR) procedures. It acts as a barrier against the migration of epithelial cells within the bone defect (performance) and thus complies with several surgical indications in the treatment of maxillofacial bone defects. It has been concluded that the risks associated with the use of this device are acceptable when weighted against the benefits to the patients. In order to improve the clinical data on the RCM, the manufacturer, Biomatlante, decided to assess that the performance and safety of the device are maintained until the reaching of its intended use. In this objective, the goal of this study will be to observe the following parameters: 1. Tissue regeneration (mucosa health on the site of implantation) 2. Safety (report of any adverse event) 3. Radiographic analysis of periodontal tissues	
Studied disease	Oral maxillofacial and periodontal defects requiring Guided Tissue Regeneration. Alveolar dental defects after tooth/teeth extraction.	
Puropose of the device	 Treatment Diagnostic Supportive care Prevention 	 Screening Health services Research Basic science Other
Study model	⊠ Single groupe □ Parallel	□ Crossover □ Factorial
Type of data	 □ Safety ⊠Safety/Efficacy □ Efficacy □ Bio-equivalence 	 Bio-availability Pharmacokinetics Pharmacokinetics/dynamics Pharmacodynamics
Number of arms	1	
Medical device used	EZ Cure TM Resorbable Collagen Membrar	ne (CE 0123)
Studied component	 Drug (including placebo) Radiation Device Behavioral 	 Biological / vaccine Genetic Procédure / surgery Dietary supplement

	□ Other	
	Category 3 : Non-interventional study.	
	This clinical investigation is prospective, multicentric and non-comparative.	
	The study is classified as category 3 according to the Jardé Law (French Law	
	relative to the Clinical Research Involving Human Persons) and thus is	
Classification of the study	qualified as "non-interventional".	
Classification of the study	Indeed, according to the terms of the protocol established in collaboration with	
	the stakeholders, this research will be carried out on a CE-marked device (CE	
	0123) and does not involve any risk or constraint since all the procedures will	

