The evaluation of the radiographic analysis of periodontal tissues will by performed before the surgery and at the 12 weeks post-surgery visit.

The details of this evaluation are the following :

- The radiographic examination is a decisive act in the establishment of the periodontal diagnosis.
- Retroalveolar plates should be used with the long cone technique.
- The necessary equipment is a 70 to 90 kv (Kilovolts) generator equipped with a long cone, Rinn angulators to parallel the film to the major axis of the tooth and standard size films for the premolar, molar and pedodontic areas for the anterior areas.
- A complete periodontal check-up includes 1 to 2 standard pictures for the premolar and molar areas of each hemiarcade, 3 to 5 pedodontic pictures for the upper and lower anterio areas and 1 to 2 "bite wing" pictures on each side.
- The interpretation of this radiographic assessment allows to make a precise examination of dental and periodontal structures.
- To examine and reassess a specific defect, the radiographic examination with a resin bite can be standardized on the Rinn angulator to reproduce the incidence.

In this study, the radiographic examination is performed in order to:

- Assess the Probing Pocket Depth (PPD): it corresponds to the distance between the top of the marginal gingiva and the bottom of the pocket
- Assess the Clinical Attachment Level (CAL): it corresponds to the distance between the enamelcementum junction and the bottom of the pocket.

For a better reproducibility of the results, the radiographies will be recorded in the eCRF and the analysis of the radiographies will be carried out by the coordinating investigator, [name] in association with the scientific expert [name].

The description of the radiographic analyses and the presentation of these results will be in a separate document from the statistical report produced by the CRO.

VII.3. MANAGEMENT OF ADVERSE EVENTS AND NEW FACT

The investigator records the adverse events or abnormal analysis results defined in the protocol as determinants for the safety assessment, keeps a documentary record and notifies the sponsor.

The investigator informs the sponsor of all adverse events that occurred in the participants.

VII.3.1. DEFINITION OF ADVERSE EVENTS

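### The radiographic secondary endpoint is defined as PPD and CAL, pocket distances that a film does not show, while crest height, which the hypothesis names, has no measure

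*Combined protocol and SAP*

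**What the plan says.** The protocol has two secondary objectives (III.2), safety and the radiographic analysis of periodontal tissues. VII.2 says what the films are for. The first purpose is "Assess the Probing Pocket Depth (PPD): it corresponds to the distance between the top of the marginal gingiva and the bottom of the pocket". The second is CAL, of which it says "it corresponds to the distance between the enamelcementum junction and the bottom of the pocket".

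The schedule in IV.3 places the PPD and CAL rows under an X-ray heading, with ticks before surgery and at V3 (12 weeks). The footnote to the baseline ticks reads "X-Ray performed at pre-inclusion or inclusion visit (before the surgery". The synopsis gives the same two time points for its X-ray measurements, and the V3 visit list in IV.6 includes an X-ray.

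PPD also appears elsewhere with another method. Footnote (b) to IV.3 describes the periodontal clinical examination and gives as its example "Probing Pocket Depth (PPD) using sensor and search for gingival inflammatory signs". That examination is ticked at V-1 only.

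The synopsis and II.3 carry parallel three-item lists of what is to be observed. The third item is "Radiographic analysis of periodontal tissues" in the synopsis and "Height preservation of the alveolar crest" in II.3.

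The synopsis, VII.2 and VIII.4.4 all say that the radiographic analyses will be described in a document separate from the CRO's statistical report. XIII.1 keeps those analyses with the coordinating investigator and the clinical expert.

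**The concern.** A film is asked for two distances that belong to a periodontal probe. If the readers follow VII.2, they either report some film distance under a probing label or find that the measure cannot be obtained. A later reader of the results could take such values for clinical probing data.

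The quantity that the hypothesis names and that a film could supply, crest height, is not defined as a variable anywhere in the endpoint or analysis sections. The two film readers could then settle what to measure after seeing the films. This would weaken one of the study's two secondary objectives.

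**Working it through.** **1. The plan's own figures.** The documents give no precision, standard deviation or rate for PPD, CAL or crest height, so no loss of precision can be calculated. The figures in VIII.1 belong to the binary mucosal endpoint, and they reproduce:

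- half-width = 1.96 × √(0.90 × 0.10 / 50) = 1.96 × 0.0424 = 0.083, against the stated 8.3%;
- recruitment = 50 / 0.90 = 55.6, rounded up to 56, as stated.

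The rest of the check compares the text.

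**2. Landmarks in VII.2.**

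| Measure | Starts at | Ends at |
|---|---|---|
| PPD | gingival margin | bottom of pocket |
| CAL | enamel-cementum junction | bottom of pocket |

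Both measures (2 of 2) end at the pocket base, and PPD also starts at a soft-tissue margin. That a plain film shows neither the gingival margin nor the pocket base is general measurement knowledge; the protocol does not say it. The enamel-cementum junction may be visible on film, so for CAL only the pocket-base end is at issue.

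**3. Method at each time point.** For the endpoint, VII.2, the X-ray block of IV.3 and its asterisk footnote, the synopsis and IV.6 all point to a film. The sensor appears only in footnote (b), as an example within an examination ticked at V-1. The V3 list in IV.6 has four items: soft-tissue control, membrane performance, X-ray and adverse events. Probing is 0 of 4. Under the schedule as written, V3 values of PPD and CAL could come only from the film.

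**4. Extraction sites.** V.1 admits alveolar bone defects after extraction. The V0 list in IV.5 puts any outstanding pre-surgery film ahead of "Periodontal surgery, tooth extraction, alveolar filling". Once a tooth has been removed, no before/after PPD or CAL can be formed at that tooth. The protocol does not say whether a neighbouring tooth would be read, and it gives no share of extraction sites, so no count of affected patients is possible.

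**5. Crest height.** Crest or bone measures named: VII.2, 0; IV.3, 0; VIII.4.4, 0. The nearest text is in II.2, which links crest height to pocket-depth comparison and adds that the same measurement was made for extraction sockets. It is past-tense literature background, is not adopted in VII or VIII, and again points to pocket depth rather than to a bone distance on film.

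**6. When the definition is fixed.** Of the three places that announce the separate radiographic document, none states a sign-off before film reading. The SAP, by contrast, must be signed before the first database lock (synopsis and VIII.4.1).

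**7. A related wording mismatch.** VIII.1 attaches the 90% target to tissue and bone regeneration. The composite in VIII.4.2 has three components (swelling, wound closure, colour), and bone is 0 of 3. The seven references cited for the target in VIII.1 are the seven listed in Table 1, which tabulates soft tissue healing.

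**The case against.** The strongest reply is that the passages governing this endpoint agree with one another. All say film at both time points, and footnote (b) belongs to a different row and offers PPD only as an example of current practice at screening. This stands against two tempting inferences. A reader might conclude that the V3 method is ambiguous between film and probe, or that a change score will mix a probed baseline with a film follow-up. The documents support neither. Their consistency does not rescue the endpoint, however, because the method they agree on does not suit the quantities they define.

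It can also be said that variables are stated: VII.2 names and defines PPD and CAL, radiographic data go into the eCRF, and VIII.4.1 promises descriptive statistics for every database variable. That is correct, and it would be wrong to say that the radiographic analysis has no variables at all. What is missing is a measure of crest height and a stated sign-off before reading.

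The two third-list items can be read as a method and a result of interest, so they need not conflict. That too is fair; the gap is that the result of interest has no measure.

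Finally, this is a descriptive secondary endpoint with no test. That limits the weight of the point but does not remove it.

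**Conclusion.** Wrong as written, on a descriptive secondary endpoint. Both named film measures are pocket distances, and crest height, part of the stated hypothesis, has no measure in the three sections where one would be expected. The definition applies to every patient's film pair. The conclusion rests on one assumption from outside the documents, about what a plain film can show. The protocol's own sensor-based description of PPD is consistent with that assumption but does not prove it.

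Two further inferences should be resisted. The bone wording in VIII.1 might suggest that the sample size is unsound. It is not: the calculation concerns the mucosal composite and reproduces, so this is a one-phrase correction. The extraction argument might suggest that a large part of the cohort is lost to this endpoint. The documents give no basis for any such proportion.

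The primary endpoint, the sample size and the safety analysis are unaffected.

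**What to change.** Reconcile II.3, IV.3 with its footnotes, IV.5 and IV.6, VII.2 and VIII.4.4. Before any film is read:

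- define the radiographic endpoint as change in alveolar crest height from the pre-surgery film to the V3 film, at a named site and against a reference visible on both films;
- allow a not-applicable category where the defect does not involve the crest;
- put this definition in the separate radiographic document and have that document signed before film reading starts;
- report PPD and CAL only as clinical probe measurements, at retained teeth, where current practice provides them.

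As a wording correction, remove the reference to bone from the 90% target in VIII.1.

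The cost is a protocol amendment, which may count as substantial and then need ethics committee endorsement under XI.2, and an eCRF field. VII.2 makes standardisation of the film geometry optional, so crest readings will be less precise where a film pair was not standardised. Not-applicable sites will reduce the number analysable for this endpoint. No new films, readers or procedures are needed.
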